## 1.6 STATISTICAL MODIFICATIONS MADE IN THE STATISTICAL ANALYSIS PLAN

The SAP Version 2 was based on Amended Clinical Trial Protocol 1. This SAP is based on Amended Clinical Trial Protocol 4 (dated 31July 2019).

- The post-treatment period has been removed from [Section 2.1.3](#), since there is no pre-specified post-treatment period in the protocol.
- The paired t-test was used for testing change from baseline and/or percent change from baseline. Because the baseline value is highly correlated with change from baseline and/or percent change from baseline, the paired t-test has been changed to analysis of covariance with baseline included as covariates as indicated in [Section 2.4.8](#).
- The definition of common TEAE, TEAE of infection, Hypersensitivity IARs and TEAE of bleeding are updated in [Section 2.1.3.1](#).
- Analyses of adverse events by place of infusion was added to this SAP in [Section 2.4.7.1.6](#).
- Subgroup analyses for efficacy endpoints was added to this SAP for patients from DFI13803 in [Section 2.4.8.15](#).
- Patient narratives as described in [Section 2.5](#) will be created, to replace various data listings.

- For Physician's global assessment of change, the 7 categories will be converted to numeric values and summarized, as described in [Section 2.4.8.6](#).

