#### **2.4.8.1 *Spleen and liver volumes***

For timing of MRI measuring spleen and liver volume, and the formula for calculating the volumes in multiples of normal (MN), refer to [Section 2.1.4.1](#).

Change from baseline and percent change from baseline for both  $\text{cm}^3$  and MN units, in addition to observed values, will be calculated and summarized for all scheduled visits. The analysis of covariance method (including baseline as covariate) and Wilcoxon-Mann-Whitney (WMW) test p-values (and 95% confidence interval) for the change from baseline and percent change from baseline will be provided in the summary tables for spleen/liver volumes in MN unit. Box plots of observed values for spleen and liver volumes in MN unit will be provided.

The correlation between spleen and liver volumes with other efficacy/safety/pharmacodynamic parameters may be explored graphically.

Analysis of covariance will be used to explore difference among different age cohorts for patients from pediatric study DFI13803, using the following model:

Percent change from baseline = age cohort + baseline

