#### **2.4.8.15 Subgroup analyses for efficacy (Patients from pediatric study DFI13803)**

For Patients from pediatric study DFI13803, below subgroup analyses will be performed.

To assess persistence of efficacy in patients with different baseline disease severity, the following subgroup analysis will be conducted:

- Spleen volume (MN) by baseline spleen volume severity (severe vs not severe). Severe patients is defined as baseline spleen volume  $>15$  multiple of normal (MN).
- % predicted DLco by baseline % predicted DLco severity (severe vs not severe). Severe patients is defined by baseline % predicted DLco  $<40\%$ .

To assess the impact of immunogenicity on efficacy, descriptive summaries for spleen volume and platelet count will be conducted for the following two groups of patients treated with olipudase alfa:

- Patients with treatment emergent anti-drug antibody (ADA) positive defined as either treatment induced or treatment boosted ADA positive at any time during olipudase alfa treatment.
- Patients with ADA negative defined as neither treatment induced or treatment boosted ADA positive at all time during olipudase alfa treatment.

For all the above subgroup analyses, within each subgroup, the change or percent change from baseline at each longitudinal time point will be summarized and analyzed with the analysis of covariance (ANCOVA) approach with baseline as covariate.

The efficacy measures (spleen volume and platelet count) will also be compared between manufacturing Process B, Process C (█) and Process C (█) as described below.

- To compare Process B and Process C (█), descriptive summaries for above efficacy measures will be created for the patients who started on Process C (█) only (patients never on Process B) versus patients who started on Process B and then switched to Process C (█) (Patients who were ever on Process B). In this analysis, the data when patients were exposed to Process C (█) will be excluded.
- Descriptive summaries for above efficacy measures will be created for the patients who did not switch to Process C (█) yet (patients never on Process C (█)) versus patients who switched to Process C (█) (Patients ever on Process C (█)).
- For patients who switched to Process C(█) and patients who switched to Process C (█) separately, the individual patient plot of observed values at each time point for above efficacy measures will be created with time point for start of each process (B, C (█) and C (█)) added on the plot.

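### SAP 2.4.8.15 asks whether antibodies affect efficacy but models ADA-positive and ADA-negative children separately, so it never estimates the difference between them

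*SAP*

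**What the plan says.** SAP 2.4.8.15 covers patients from DFI13803. Its ADA paragraph opens: "To assess the impact of immunogenicity on efficacy, descriptive summaries for spleen volume and platelet count will be conducted". It forms two groups: children with treatment-induced or treatment-boosted ADA at any time on olipudase alfa, and children with neither at any time.

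One sentence then governs both the ADA and the severity subgroups: "within each subgroup, the change or percent change from baseline at each longitudinal time point will be summarized and analyzed", using the "analysis of covariance (ANCOVA) approach with baseline as covariate". There is no subgroup term, contrast or interval for a difference.

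Three other places bear on the reading:

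- For age cohorts, SAP 2.4.8.1 does specify a between-group model for spleen and liver volume: "Percent change from baseline = age cohort + baseline". SAP 2.4.8.2 and 2.4.8.7 do the same for pulmonary function and for platelets and hemoglobin.
- SAP 1.6 explains where the ANCOVA came from: "The paired t-test was used for testing change from baseline and/or percent change from baseline", and was replaced because baseline correlates with change.
- The severity subgroups have a different aim: "To assess persistence of efficacy in patients with different baseline disease severity".

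**The concern.** Whether antibodies affect efficacy is a question about two groups: do children who develop ADA respond differently from those who do not? A model fitted inside one group estimates only that group's mean change. Two such estimates side by side give neither the size of the gap nor its uncertainty, and the reader is left to compare them by eye or by significance.

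That comparison can fail in both directions. If antibodies go with a much smaller benefit but both groups still improve, the output looks reassuring. If the groups respond alike but one is very small, the small one may miss significance and the output looks like an antibody effect. Immunogenicity is a standing question for an enzyme replacement therapy, so a misleading answer would matter even in a secondary analysis.

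**Working it through.** The documents give no alpha, SD, effect size or ADA split for this analysis, so there is no planned figure to reproduce. What follows is illustration.

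**Inputs.** Pediatric N is about 20 (SAP 1.1) or 12 (SAP 1.3 and 2.4). Assumed: two-sided alpha 0.05, residual SD of percent change 12 points, and the splits shown.

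**Formulas.**
- Within one group of n, with baseline centred: noncentral t, n - 2 df, noncentrality = (|mean change| / SD) × √n.
- Pooled model with group and baseline: noncentral t, N - 3 df, noncentrality = (|difference| / SD) / √(1/n1 + 1/n2), ignoring the small loss from baseline imbalance.
- 95% half-width of the difference, in SD units: t(0.975, N - 3) × √(1/n1 + 1/n2).

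**A real difference hidden.** True mean change -25% in 8 ADA-positive patients and -50% in 12 ADA-negative patients.
- n = 8: 25/12 = 2.083; 2.083 × √8 = 5.89; 6 df, critical t 2.447; power 99.8%.
- n = 12: 50/12 = 4.167; 4.167 × √12 = 14.4; power about 100%.
- Both significant: about 99.8%.
- Pooled contrast: 2.083 / √(1/8 + 1/12) = 2.083 / 0.456 = 4.56; 17 df; power about 99%. A simulation of 3000 trials, which includes baseline imbalance, gave 98.5%.
- Half-width: 2.110 × 0.456 = 0.96 SD, and 0.96 × 12 ≈ 11.6 points. A 25-point gap would be reported as roughly 13 to 37 points.

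The same holds in SD units. With effects of 3 SD and 1.5 SD in groups of 10 and 10, both are significant 98.5% of the time, while the contrast has 88.5% power. In groups of 6 and 6 the figures are 78% and 64%.

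**Equal response, apparent disagreement.** Chance that exactly one group is significant, p(1 - q) + q(1 - p), where p and q are the two within-group powers:

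| Split | True change in both | Power, larger group | Power, smaller group | Disagree |
|---|---|---|---|---|
| 17 / 3 | -40% | ~100% | 35% | 65% |
| 16 / 4 | -25% | ~100% | 59% | 41% |
| 16 / 4 | -40% | ~100% | 89% | 11% |
| 14 / 6 | -25% | ~100% | 96% | 4% |
| 12 / 8 | -25% | ~100% | 99.8% | 0.2% |
| 14 / 6 | -40% | ~100% | ~100% | ~0% |

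The pooled contrast has a 5% error rate at every split. With weaker effects (mean change of 1 SD) disagreement is larger: 33% at 10/10 and 53% at 14/6.

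**Precision of the pooled contrast.**
- N = 20, t = 2.110: 10/10, 0.94 SD; 14/6, 1.03; 16/4, 1.18; 17/3, 1.32.
- N = 12, t = 2.262: 6/6, 1.31 SD; 8/4, 1.39; 9/3, 1.51.
- Difference detectable with 80% power: 1.33 to 1.86 SD at N = 20, and 1.82 to 2.10 SD at N = 12.

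**Should severity get the same term?** Severity is a cut of the outcome's own baseline (spleen above 15 MN; predicted DLco below 40%). Simulating 20 patients with baseline N(15, 5), slope -0.5, SD 12 and a cut at 15 MN, severe and non-severe patients differ by about 4 points unadjusted. With baseline also in the model, the severity coefficient averages about 0 and its standard error is about 1.7 times larger (half-width about 20 points against 11.5). The term would adjust away what it is meant to measure.

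**The case against.** The strongest reply is that SAP 2.4.8.15 describes the ADA work as descriptive and names no p-value, null hypothesis or alpha. Reading the ANCOVA as a test of change against zero is an inference from SAP 1.6, where it replaces the paired t-test, and from SAP 2.4.8.1, where the overall spleen and liver tables carry "test p-values (and 95% confidence interval) for the change from baseline and percent change from baseline will be provided in the summary tables". Nothing says that ADA impact will be judged by comparing significance between the groups. This limits the point but does not remove it. The governing sentence still applies a model to the ADA groups, whereas the process comparison later in the section ("The efficacy measures (spleen volume and platelet count) will also be compared between manufacturing Process B") has summaries and plots only. Whether or not p-values are printed, no difference is estimated.

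A second reply is that disagreement under equal response depends on the split. That stands: the high figures need 3 or 4 patients in one group, and at 14/6 or 12/8, with the changes assumed in the table, the rate is 4% or less. Hiding a real difference does not need small groups.

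A third is that ADA status is fixed by antibodies at any time after baseline, so an early-visit contrast may classify a child by antibodies that appear later. That stands too. A between-group estimate would be an association, not an effect of antibodies.

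A reader might also infer that the severity analysis has the same fault. The documents do not support that. Its stated aim is persistence of efficacy in patients of differing severity, which change from baseline within each stratum does address, and the SAP claims no comparison between strata.

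**Conclusion.** The point holds for the ADA subgroups. The stated aim needs a comparison, the planned model gives none, and for both outcomes concerned the SAP already has a suitable model for age cohorts. Under the assumed SD of 12 points, a benefit of -25% against -50% would appear as two significant improvements in about 99.8% of trials. Chance disagreement under equal response is a material risk (11% to 65% in the cases computed) if one group has 3 or 4 patients, and minor with larger groups and large effects. All of these figures rest on assumed SD, alpha, effects and splits.

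The documents do not support two stronger readings: that the SAP commits to judging ADA impact by subgroup p-values, or that the severity strata are wrongly analysed. The matter is worth correcting, but it concerns an exploratory analysis of secondary endpoints in an open-label study whose primary objective is safety.

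**What to change.** In SAP 2.4.8.15, for spleen volume and platelet count, add the model: change or percent change from baseline = ADA group + baseline. Report the adjusted difference with its 95% CI at each visit. Base any statement on the impact of ADA on that interval, and keep the within-group results as description. Label the contrast exploratory and non-causal, because ADA status is defined over the whole treatment period.

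Leave the severity subgroups as within-stratum summaries. Do not add a severity term adjusted for the baseline that defines it. One sentence saying that no between-stratum inference is intended would prevent misreading.

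The cost is one model term and a short wording change, with no new data. The drawback is imprecision: half-widths of about 0.9 to 1.3 SD with 20 patients and 1.3 to 1.5 SD with 12, so the result should be read as an estimate and not as a powered test.

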## **2.4 STATISTICAL METHODS**

Data collected in this study will be presented using summary tables, figures, and data listings. Descriptive statistics for categorical variables will be provided using frequencies (n) and percentages (%). Descriptive statistics for continuous variables will be provided using number of observations (n), mean, standard deviation (SD), median, minimum, and maximum. All data used in tabular summaries or figures will be supported by listings of underlying data – raw and/or derived, and all figures will be supported by relevant summary information.

All summaries will be provided for the LTS population, along with separate subgroups in the population according to which original study the patient belonged to: DFI13412 (adult study, Phase 1B, 26 weeks, 5 patients), DFI13803 (pediatric study, Phase 1/2, 64 weeks, 12 patients). In addition, similar summaries will be produced by age cohort of adolescent, child, infant for the patients who transition from pediatric study DFI13803.

The scheduled visits in statistical displays will be labelled in months of total follow up time from the first infusion in the original study. For example, a 6-month visit in this study for a patient transitioning from the 26-week DFI13412 study will be identified as Month 12 exposure in the displays. The schedule of measurements for this study will be followed for display presentation with baseline derived from the original study. For patients in this study, the results from the original study visits will be included, unless specified otherwise, for the purpose of understanding the continuity of treatment effect during this extension phase; for details and descriptions of all results from the original study, please refer to the original study CSR. For parameters that are not collected in the extension phase will not be part of this SAP.

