#### **2.4.7.1.6 Analyses of adverse events by place of infusion**

To assess the comparability between site infusion and home infusion, the following adverse events will be analyzed, pooling patients of different age cohorts. Only adverse events that occurred after the date when the first patient in the study received his/her first home infusion will be included in these analyses.

- Overview of treatment-emergent adverse events
- Treatment-emergent adverse events by SOC and PT
- Treatment-emergent adverse events by severity, and by SOC and PT
- Treatment-emergent adverse events by the latest infusion dose, and by SOC and PT
- Treatment-emergent serious adverse events by SOC and PT
- Protocol defined IARs by SOC and PT
- Protocol defined IARs by severity, and by SOC and PT
- Protocol-defined IARs started during infusion by SOC and PT
- Protocol-defined IARs started between 0 hours (exclusive) and 3 hours (exclusive) post end of infusion
- Protocol-defined IARs started between 3 hours (inclusive) and 24 hours (inclusive) post end of infusion
- Protocol-defined IARs started between 24 hours (exclusive) and 72 hours (inclusive) post end of infusion
- Protocol-defined IARs started after 72 hours post end of infusion
- Algorithm-defined IARs

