#### **2.4.8.7 Hematology**

Platelet and hemoglobin are efficacy parameters. At every six month clinic visit these two parameters are evaluated from two blood samples - one for complete blood count, one for hemogram. The average of these two values will be used for efficacy analysis. If and when two values are not available, the single available value will be used.

Observed values, change from baseline and percent change from baseline will be summarized at each scheduled time point. Summary plots of pre-infusion values over time will be provided. By-patient plots over time will also be provided.

For platelet and hemoglobin, analysis of covariance will be used to explore difference among different age cohorts for patients from pediatric study DFI13803, using the following model:

Percent change from baseline in platelets = age cohort + baseline

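### The never-versus-ever-switched summary in SAP 2.4.8.15 is not limited to post-switch values in the ever-switched group, so it can dilute any change in spleen volume or platelets after the switch

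*SAP*

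**What the plan says.** The aim in SAP 2.4.8.15 is a comparison by product: "The efficacy measures (spleen volume and platelet count) will also be compared between manufacturing Process B" and two Process C versions. Three items follow.

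- **Process B item.** Children who started on a Process C product are set against children who started on Process B and later switched. An exclusion by exposure, opening "In this analysis, the data when patients were exposed to Process C", applies to this item only.
- **Never-versus-ever item.** "Descriptive summaries for above efficacy measures will be created for the patients who did not switch to Process C" at the time of analysis, against children who did switch. No limit on which of their values count is stated.
- **Plots.** Individual plots of observed values for switched children, with the start of each process marked.

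The general rules are in SAP 2.4. On the time axis: "The scheduled visits in statistical displays will be labelled in months of total follow up time from the first infusion in the original study". On inclusion: "For patients in this study, the results from the original study visits will be included, unless specified otherwise". SAP 2.6.3 analyses by nominal visit. For layout, SAP 2.4.8.1 lists change and percent change in spleen volume, which "in addition to observed values, will be calculated and summarized for all scheduled visits". SAP 2.4.8.7 says of platelets and hemoglobin: "Observed values, change from baseline and percent change from baseline will be summarized at each scheduled time point".

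**The concern.** The stated question is whether spleen volume and platelets look the same on different products. The grouping answers a different one: whether children who at some time received the product differ from children who never did. A child who switched late brings a long record on an earlier product into the ever-switched column, and the time axis does not show where that record ends.

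If the product change altered either measure, the ever-switched mean would show only part of the alteration at any visit where some of these children had not yet switched. A reader could then take an attenuated difference as reassurance that the products perform alike. SAP 2.4.7.11 sends immunogenicity and safety by process to integrated summaries. For efficacy by process, the tables of 2.4.8.15 are the only ones I find in the SAP. SAP 3 allows an interim report to support regulatory approval, and at an early data cut fewer visits fall after the last switch.

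**Working it through.** The plan gives no figure to reproduce: there is no sample size, margin, test or effect size for this comparison. The check is a reading of the rules followed by mixture arithmetic.

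**1. Does any rule limit the ever-switched values?** The item itself has none. The exclusion in the Process B item is confined to that analysis. SAP 2.4 includes earlier visits by default, and SAP 2.6.3 does not re-index visits to the switch. So pre-switch values enter. The label is redacted, but the limit is absent whichever version is meant.

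**2. Effect at one visit.** Let p be the share of ever-switched children at that visit who have not yet switched, and d the post-switch shift. Assume d is immediate and constant, and that early and late switchers are otherwise alike.

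Ever-switched mean = p × (earlier mean) + (1 - p) × (earlier mean + d) = earlier mean + (1 - p) × d

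| p | share of d shown | for an assumed d of 10 points |
|---|---|---|
| 0% | 100% | 10 |
| 25% | 75% | 7.5 |
| 50% | 50% | 5.0 |
| 75% | 25% | 2.5 |
| 100% | 0% | 0 |

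**3. A small illustration (switch dates assumed).** Six children switch one each at Months 24, 30, 36, 42, 48 and 54, and a visit in the switch month counts as pre-switch. Of a 10-point shift the table shows:

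- Month 24: 0/6 switched, 0 points
- Month 36: 2/6 switched, 3.3 points
- Month 48: 4/6 switched, 6.7 points
- Month 60: 6/6 switched, 10 points

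**4. How many visits could be mixed (spread assumed).** If exposure at switch is spread evenly over S months starting at Month a, then p(m) = (a + S - m)/S inside that window. The expected number of mixed visits is S/12 for annual MRI (the routine pediatric spacing after Year 2) and S/6 for six-monthly platelets:

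| S (months) | annual spleen visits | six-monthly platelet visits |
|---|---|---|
| 12 | 1 | 2 |
| 24 | 2 | 4 |
| 36 | 3 | 6 |

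The count is one lower when the window starts and ends exactly on a scheduled visit. For example, with a = 36 and S = 24: p(42) = 18/24 = 75%, p(48) = 12/24 = 50%, p(54) = 6/24 = 25%, p(60) = 0.

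**5. Scans outside this count.** Protocol Table 8 footnote i adds an MRI at the first 6-month visit after a switch beyond Year 2, when that visit is not already annual. Such a scan is post-switch for the change that triggered it, so the spleen counts in step 4 cover annual scans only.

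**The case against.** The best defence is that the section groups by patient throughout. The Process B item also does so: its ever-on-B group spans Process B and Process C periods, and its exclusion removes only one Process C product's data. A reader might infer that the Process B item handles exposure cleanly and that the next item simply forgot to. The documents do not support that. Nor is the home-infusion analysis in SAP 2.4.7.1.6 a model for a per-child cut: its rule, "Only adverse events that occurred after the date when the first patient in the study received his/her first home infusion will be included", is a single study-wide date.

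It is also fair that the by-visit layout is inferred. The sentence in 2.4.8.15 that asks for each longitudinal time point covers the severity and antibody subgroups, not the process items. A table of last available values only would avoid the mixing, but the item does not say that it is one.

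The individual plots do show before and after within each child, and SAP 2.4 requires listings behind every table. With approximately 20 children, the plots may be the more informative display. This lowers the weight of the point. It does not change what the group table reports under the product's name.

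**Conclusion.** The point holds and is minor. The grouping rule does not deliver the comparison by product that the section announces. At a mixed visit the ever-switched summary shows (1 - p) of any post-switch change, and before the first switch it contains no data on the named product.

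This rests on the by-visit layout of SAP 2.4.8.1 and 2.4.8.7, on an immediate and constant shift, and on no other difference between groups. The documents give no switch dates, so the number of mixed visits is unknown and the spreads above are illustrations. Visits after the last switch are unaffected.

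A reader might go further and infer that the plan would support a false claim of comparability. The documents do not bear that out: these are descriptive summaries with no test, margin or equivalence claim, and they belong to a secondary objective. The primary safety objective is untouched.

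**What to change.** Add one or two sentences to the never-versus-ever item of SAP 2.4.8.15. For children who switched, divide spleen volumes and platelet counts at the first infusion of the named product, report pre-switch and post-switch values separately, and summarize within-child change from the last pre-switch value by time since switch. Indexing to the switch is better than a post-switch row by exposure month, because that row would hold only the children who had switched by then and its make-up would change from visit to visit.

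The change re-tabulates values already collected. Table 8 footnote g schedules platelet samples 3 months after either switch, and footnote i the MRI described above. Under Table 7, which applies before the second database lock changes, footnote i names only a manufacturing scale change, so some switches may have no extra scan and would rely on the next annual one.

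The cost is few values per cell (approximately 20 children in SAP 1.1, although SAP 1.3 and 2.4 still say 12). Early switchers will also be over-represented at longer times since switch, so each cell should show its number of children.
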